12.2.2 Intent-to-Treat (ITT)

The intent-to-treat population (ITT) will consist of any subjects that have signed the ICF, meet study eligibility criteria, and are randomized to the treatment or control arm of the study.

12.2.3 Modified Intent-to-Treat (mITT)

Subjects will be included in the Modified Intent-to-Treat group if they sign the ICF, meet study eligibility criteria, are randomized, and in the treatment group receive monitoring for the first 72 hours of study enrollment or until ICU discharge, whichever occurs first. The mITT population represents the Primary and Secondary Analysis population for this study.

12.2.4 Per-Protocol (PP)

Subjects will be included in the Per-protocol group if they sign the ICF, are randomized and have the assigned procedure completed, meet critical study eligibility criteria and have no major protocol deviations (defined in the Statistical Analysis Plan), and, in the treatment group, receive monitoring for the first 72 hours of study enrollment. The PP population represents a subgroup analysis population for this study.

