### 6.2 INTENT TO TREAT POPULATION (ITT)

The intent-to-treat (ITT) population for this study includes subjects that are enrolled in the study, have signed the ICF, meet study eligibility criteria, and have been randomized to either the treatment or control arm of the study.

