### 6.4 PER-PROTOCOL (PP)

Subjects will be included in the Per-protocol group if they sign the ICF, are randomized and have the assigned procedure completed, meet critical study eligibility criteria and have no major protocol deviations (to be pre-defined as an attachment to the interim and final analyses), and, in the treatment group, receive monitoring for the first 72 hours of study enrollment. The PP population represents the primary analysis population for the primary and secondary endpoints.

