### 6.5 SAFETY

Subject will be included in the safety group if they are in the ITT analysis population and study treatment was at least attempted. This is the primary analysis population for safety, including adverse events (this is a change from the protocol, where it states that adverse events will be reported on all enrolled patients; it has been since felt that this could underreport the true adverse event rates in patients to whom randomized treatment was attempted). Patients are analyzed under the treatment received.

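### The per-protocol set applies a looser eligibility test than ITT and mITT, so the SAP's primary efficacy set is not guaranteed to lie within them

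*Protocol*

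**What the plan says.** Protocol 12.2.2 limits ITT to consented subjects who "meet study eligibility criteria, and are randomized to the treatment or control arm of the study". SAP 6.2 says the same: subjects must "have signed the ICF, meet study eligibility criteria, and have been randomized to either the treatment or control arm of the study". For mITT, protocol 12.2.3 requires that subjects "meet study eligibility criteria, are randomized, and in the treatment group receive monitoring for the first 72 hours" or until ICU discharge, and SAP 6.3 agrees. None of these four definitions qualifies the eligibility condition.

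PP is worded differently. Under protocol 12.2.4, PP subjects "are randomized and have the assigned procedure completed, meet critical study eligibility criteria and have no major protocol deviations", and SAP 6.4 repeats the restriction to critical criteria. Neither document says which of the 5 inclusion and 27 exclusion criteria are critical. The protocol says that major deviations are defined in the SAP. The SAP defers them to an attachment to the interim and final analyses.

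On the roles of the sets, SAP 6.4 states: "The PP population represents the primary analysis population for the primary and secondary endpoints". SAP Section 9 makes mITT supportive. SAP 6.5 adds: "Subject will be included in the safety group if they are in the ITT analysis population and study treatment was at least attempted". SAP Section 10 runs the adverse event analyses on mITT and Safety.

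**The concern.** A per-protocol set is normally a subset of the set it is compared with, so that a difference between the two reflects the subjects whom PP left out. Here PP is looser on eligibility, so it may also contain subjects whom mITT rejects. A difference between PP and mITT could then mix exclusions with additions.

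Two further consequences come from the eligibility condition inside ITT and mITT, whatever PP says.

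- A randomised and treated subject later found ineligible drops out of ITT, and so out of Safety. SAP 6.5 gives as its reason for creating the Safety set a worry about under-reporting event rates in subjects in whom treatment was attempted. Dropping treated subjects works against that aim.
- Some criteria concern what happens once the subject is randomised or on treatment. Events after allocation could then decide who belongs to ITT.

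**Working it through.** No figure in the plan bears on this point, so there is none to reproduce. The check sets the definitions side by side and applies them.

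| Set | Where | Eligibility condition | Further conditions (all need consent and randomisation) |
|---|---|---|---|
| ITT | Protocol 12.2.2; SAP 6.2 | Unqualified | None |
| mITT | Protocol 12.2.3; SAP 6.3 | Unqualified | Starling arm: monitored to 72 h or ICU discharge |
| PP | Protocol 12.2.4; SAP 6.4 | Critical criteria only | Procedure completed; no major deviation; Starling arm: monitored to 72 h |
| Safety | SAP 6.5 | Inherited from ITT | Treatment attempted |

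**Step 1: a test subject.** Take a randomised subject who fails one non-critical criterion, completes the assigned procedure, has no deviation graded major and, if in the Starling arm, is monitored for 72 hours. PP: in. ITT: out, on eligibility. mITT: out, for the same reason. Safety: out, because not in ITT.

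**Step 2: all combinations.** Treat each condition as met or not met, with all criteria met implying critical criteria met, and count the profiles that qualify for PP.

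- Starling arm: every PP condition is fixed except whether the non-critical criteria are also met, giving 2 profiles.
- Control arm: monitoring is not a condition, so there are 3 monitoring states × 2 = 6 profiles.
- Total: 2 + 6 = 8. Of these, 1 + 3 = 4 fail a non-critical criterion and lie outside ITT, mITT and Safety.
- If every eligibility failure counted as a major deviation, 4 PP profiles would remain and 0 would lie outside.

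These are counts of logical profiles, not of patients. On monitoring, PP is stricter than mITT, so the break arises on eligibility alone.

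**Step 3: can such a subject occur?** Protocol 14.2 and SAP 7.4 both list enrolment of a subject who did not meet the criteria as a deviation or violation, and neither grades it. Protocol 8.7 makes incorrect enrolment a possible reason for discontinuation, not a mandatory one. Exclusion 12 (treatment protocol cannot be started within 1 hour after randomisation) and exclusion 26 (treatment departs from the algorithm) concern events at or after the start of treatment.

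**Step 4: internal consistency.** SAP 7.4 will tabulate each violation type, including ineligible enrolment, for the ITT set. Under SAP 6.2 that set contains no ineligible subjects, so the row is zero by definition. The table works only if ITT includes randomised subjects who turn out to be ineligible.

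**The case against.** The strongest reply is that the gap may never open. PP also requires freedom from major deviations. If the attachment promised in SAP 6.4 grades every eligibility failure as major, PP nests on eligibility. That stands, and it is why the point is that nesting is not guaranteed. The word *critical* would then have no effect, however, and the attachment is not part of either document.

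The route is also narrow. Consented subjects found ineligible are screen failures and exit (protocol 8.1). So do subjects not admitted to the ICU or given more than 3 L before randomisation (8.6). Incorrectly enrolled subjects may be discontinued (8.7). This limits the number but does not make it zero.

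Some tempting inferences go too far.

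- A reader might conclude that agreement between PP and mITT tells us nothing. Sensitivity sets need not be nested, and agreement between overlapping sets is still informative. What is lost is a clean attribution of any difference.
- A reader might say that the disposition table fails. SAP 7.2 bases its population percentages on enrolled subjects and adds an accountability listing, so the table does not need nested sets.
- A reader might say that safety data vanish. The listings in SAP 10.1 (all adverse events) and 10.3 (deaths) would still show these subjects. The gap is in the summary tables that Section 10 assigns to mITT and Safety, and it comes from the eligibility condition in ITT, not from the wording of PP.

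Finally, the effect on efficacy matters mainly because the SAP makes PP primary. Protocol 12.2.3 names mITT as primary, and 12.2.4 treats PP as a subgroup population. Restoring those roles would remove most of that harm, but not the loss of randomised subjects from ITT or the conflict with SAP 7.4.

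**Conclusion.** The wording defect is real and appears in both documents. As written, a subject can belong to the SAP's primary efficacy set and to none of ITT, mITT or Safety, and randomised subjects can leave ITT because of events after allocation. The conclusion assumes that *critical* means fewer than all the criteria and that at least some eligibility failures will not be graded major.

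The number of subjects affected cannot be derived from the documents and is probably small. A reader might assume that 5 to 10% of randomised subjects fail a non-critical criterion, giving 0.05 × 120 = 6 to 0.10 × 120 = 12 subjects, or 10.5 to 21 of 210. Nothing in the documents supports such a rate, and the counts would be ceilings, since they suppose that every such subject passes all the other PP conditions. No effect on the estimate, the power or the type I error has been shown. The point should be corrected because the definitions contradict the SAP's own violation table and the repair is cheap.

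**What to change.** - In protocol 12.2.2 and 12.2.3 and SAP 6.2 and 6.3, delete the eligibility condition. ITT becomes all randomised subjects by assigned arm, and mITT adds only its monitoring condition.
- Begin protocol 12.2.4 and SAP 6.4 with *mITT subjects who also …*.
- List the critical eligibility criteria and the major deviations before any analysis.

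PP then lies within mITT and mITT within ITT. The Safety set, defined through ITT, keeps treated subjects who prove ineligible, and the violation table in SAP 7.4 makes sense.

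This is six wording edits plus the two lists. The downside is that a few ineligible randomised subjects enter ITT and mITT. Some may have been discontinued and have missing outcomes, which adds to the missing data.

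A smaller change, deleting *critical* from the two PP definitions, would restore nesting on eligibility with two edits. It would still leave randomised subjects outside ITT and Safety, and the conflict with SAP 7.4 would remain.

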12.3 Primary Endpoint Analysis

The primary endpoint is an evaluation of the difference between the two treatment groups in mean fluid balance (L) at 72 hours or ICU discharge, whichever occurs first. The following hypothesis will be tested:

$$H_0: \mu_C - \mu_T = 0$$

$$H_a: \mu_C - \mu_T \neq 0$$

where μ_T and μ_C is the average fluid balance in the Starling SV and control groups, respectively. Statistical summaries will include means, medians, and standard deviation, as well as 95% confidence intervals. A t-test for superiority at a significance level of 0.025 will be performed to test the hypothesis that μ_T is significantly less than μ_C . If it can be established that the difference is greater than 0 points (i.e. $\mu_C > \mu_T$), superiority will also be claimed.

12.4 Secondary and Exploratory Endpoints

Secondary objectives that have been pre-specified to be included in the formal statistical analysis will be tested in sequential fashion using the Holms step-down procedure for type-I error rate correction if and only if the primary objective passes according to the criteria outlined above. At the conclusion of the trial, the key secondary endpoints will be ordered sequentially from most significant to least significant. The endpoints will then be tested in order at adjusted levels of significance (i.e. E1: 0.05/k, E2: 0.05/k-1; E3: 0.05/k-2, where k=number of specified endpoints). Once an endpoint fails, all following endpoints will not be tested. Following is a list of key secondary endpoints:

Following is a list of key secondary endpoints for formal testing:

- Length of ICU stay (days) until subject is medically ready for discharge
- Number of days free from ventilator use (30 day period)
- Requirement for mechanical ventilation
- Number of days free from vasopressor use
- Changes in serum creatinine levels from baseline
- Requirement for renal replacement therapy (RRT)

Additional secondary endpoint have also been identified for testing, but will not be included in the formal statistical testing procedures for key secondary endpoints:

- Incidence of Adverse Events (AE)

- Number of ICU readmissions
- Mortality rate
- Mean volume of treatment fluid
- Incidence of Major Adverse Cardiac Event (MACE)
- Discharge location
- Mean difference in fluid balance at ICU discharge

Additional sub-analyses have been planned for the primary and key secondary endpoints. Primary and secondary endpoints will also be evaluated by the following subgroup analysis:

- Patient disease state
- Patients determined to be fluid responsive vs non-fluid responsive
- AKI measures in patients determined to increase serum creatinine levels from baseline vs decrease serum creatinine levels from baseline
- Enrollment time frame

12.5 Baseline Data Summary

Baseline data including subject demographics, clinical history, risk factors, and pre-procedure patient characteristics will be summarized using descriptive statistics (e.g., mean, median, standard deviation, 25th percentile, 75th percentile, minimum and maximum) for continuous variables and frequency tables or percentages for categorical variables.

12.6 Subject Accountability and Missing Data

Subjects enrolled in this study are followed for a short time period, and missing data in this study is expected to occur at a low rate. All efforts will be used to prevent missing data. These efforts include, but are not limited to, complete site training and regular monitoring to help to minimize missing data.

Subjects without the minimum amount of monitoring [i.e. throughout first 72 hours of study enrollment,] and measurements specified in the protocol will be considered as missing in the final analysis. The impact of missing data on the study will be evaluated via sensitivity analyses if more than 5% of subjects do not have evaluable data for the primary outcome. In the final report, the number and proportion of subjects eligible for and compliant with each analysis population will be presented.

13. DATA HANDLING AND RECORD KEEPING

Each participating site will maintain appropriate medical and research records for this trial, in compliance with regulatory and institutional requirements for the protection of confidentiality of subjects. As part of participating in a manufacturer-sponsored study, each site will permit authorized representatives of the Sponsor(s), the Sponsor's designee, and regulatory agencies to examine (and when required by applicable law, to copy) clinical records for the purposes of quality assurance reviews, audits, and evaluation of the study safety and progress.

Source data are all information, original records of clinical findings, observations, or other activities in a study necessary for the reconstruction and evaluation of the trial.

13.1 Clinical Data Collection

Electronic Case Report Forms (eCRFs) will be used to collect all subject data during the course of the study and will be entered into an electronic database. eCRFs must be fully completed for each subject and signed by the Investigator when complete.

Good Clinical Practice Guidelines require that Investigators maintain information in the study subject's medical records that corroborate data collected on the eCRFs. In order to comply with these regulatory requirements, the following information should be maintained:

- Medical history/physical condition of the study subject before involvement in the study sufficient to verify protocol entry criteria.
- Dated and signed notes on the day of entry into the study including the study investigator, study name, subject number assigned and a statement that consent was obtained.
- Dated and signed notes from each study subject visit with reference to the eCRFs for further information, if appropriate (for specific results of procedures and exams).
- Information related to adverse events.
- Study subject's condition upon completion of or withdrawal from the study.
- Discharge summaries/procedure reports.

13.2 Data Reporting

All site Investigators or designated individuals shall be responsible for recording all study data on the eCRFs. The Investigator is required to electronically sign the eCRFs to verify that he/she has reviewed and agrees with the recorded data. All protocol deviations shall be documented and a justification for any missed assessments shall be provided on the Protocol Deviation eCRF.

Completed eCRFs will be verified by the monitor at the investigational sites or by remote monitoring as at regular intervals throughout the study, as outlined in the Monitoring Plan. The Investigator will allow the monitor and/or representative of the Sponsor, and any regulatory body to review and inspect the study files, subject eCRFs, subject medical records and other related study documents as required.

13.3 Data Review

eCRFs will be reviewed for completeness and clarity. Missing or unclear data will be investigated by the monitor and will be retrieved, clarified and entered by study personnel as necessary throughout the study. Cheetah Medical, or designee, may request additional documentation from the Investigator such as physician notes or physician written summaries when adverse events are observed and reported. Documentation provided will also be used for the adjudication of specified adverse events by the Independent Safety Physician.

Development of the data collection system for the study will be performed by Cheetah Medical, or designee. Cheetah Medical, or designee will also be responsible for the quality control of the database and confirming the overall integrity of the data.

13.4 Investigator Records

Investigators will maintain complete, accurate and current study records. The following records must be maintained in designated study files:

- Clinical protocol and all amendments
- Signed Clinical Trial Research Agreement
- Institutional Review Board (IRB) Approval Letter(s)
- IRB approved informed consent(s) (including any revisions)
- CV for all Investigators, signed and dated
- Investigator(s) medical license
- Financial Disclosure Form for all Investigators
- Correspondence relating to this study
- Correspondence with the IRB
- IRB membership list and/or assurance number
- Delegation of Authority log
- Device Instructions for Use
- Printed copy of blank set of CRFs
- Subject Log
- Site Visit Log (e.g. for Monitor sign-in)
- Site Training records
- Investigational Device Accountability Logs
- Reports (includes Adverse Event reports and final reports from Investigator and Sponsor)
- Copy of all IRB approved subject-related materials and/or study advertising materials

The following records must be maintained for each subject enrolled in the study:

- Signed subject consent forms
- Copy of final completed CRFs
- Record of any adverse events with supporting documentation
- Reports, progress notes, physician and/or nursing notes, and subject office files
- Records pertaining to subject deaths throughout the course of the study

13.5 Data Retention

Study documents should be retained for a minimum of 5 years. These documents should be retained for a longer period, however, if required by local regulations. No records will be destroyed without the written consent of the Sponsor, if applicable. It is the responsibility of the Sponsor to inform the Investigator when these documents no longer need to be retained.

Table 2: Responsibilities for Preparing and Submitting Reports

Type of Report	Prepared by Investigator for	Time of Notification
Enrollment Notification Form	Sponsor	Within 24 hours of procedure
Electronic Case Report Forms	Sponsor	Within 10 working days
Serious/ Device Related Adverse Event	Sponsor and IRB (as required)	Within 24 hours of knowledge or as required by IRB
Subject Death	Sponsor and IRB (as required)	Within 24 hours of knowledge
Subject Withdrawal	Sponsor	Within 24 hours of knowledge
Withdrawal of IRB Approval	Sponsor	Within 24 hours of knowledge
Protocol Deviations	Sponsor and IRB	Within 5 working days of occurrence or knowledge
Informed Consent Not Obtained	Sponsor and IRB	Within 24 hours of knowledge or as required by IRB
Final summary report	Sponsor and IRB and Regulatory Authority (as required)	Within 3 months of study completion

13.6 Investigator Reports

Each year an annual summary report shall be prepared by the Investigator which provides a summary of the number of subjects treated to date as well as other pertinent clinical information associated with the investigational procedure. The annual report is required to be provided to the IRB and the Sponsor or designee.

Upon completion and/or termination of the study a final report shall be prepared. This report will contain a critical evaluation of all data collected during the course of the investigation at each institution. The Sponsor or its designee is responsible for preparing this compilation to Investigators for submittal as a final report to their reviewing IRB.

14. QUALITY CONTROL AND ASSURANCE

14.1 Site and Investigator Selection

The Sponsor selects qualified investigators with appropriate experience with this patient population at health care facilities with adequate resources to participate in this study. Investigational sites will be selected using combined current assessments of site and investigator qualifications.

14.2 Protocol Deviations

An investigator is not allowed to deviate from the Protocol if the deviation affects subject's rights, safety and wellbeing, or the scientific integrity of the clinical investigation. Under

emergency circumstances, deviations from the protocol to protect the rights, safety and well-being of human subjects may proceed without prior approval of the Sponsor and the IRB.

A protocol deviation is a failure to comply with the requirements specified within this clinical study protocol. Examples of protocol deviations may include enrollment of a study subject who does not meet all of the inclusion/exclusion criteria specified in the protocol and missed study visits without documentation. Each investigator shall conduct this clinical study in accordance with this clinical study protocol, regulatory body regulations, Good Clinical Practices.

All deviations are reviewed and assessed for their impact on subject safety by the Sponsor or designee. The PI and study staff is responsible for knowing and adhering to their IRB reporting requirements.

The protocol deviations for this protocol consist of, but not limited to the following:

- Failure to obtain subject's informed consent prior to any study-related activities;
- Subject did not meet the inclusion and/or exclusion criteria and were enrolled;
- Failure to conduct protocol required clinical test or assessment;
- Failure to complete protocol required assessments within the required time frame
- Failure to report serious adverse events according to protocol requirements.

In the event of any deviation from the protocol, the Investigator will be notified of the site's non-compliance. Corrective actions will be required, if necessary. Continued protocol deviations despite re-education of the study site personnel or persistent protocol deviation may result in termination of the site's study participation. Subjects enrolled at these sites will continue to be followed per the clinical protocol.

